8.3.5 Suicidal Ideation and Behavior Risk Monitoring (Columbia-Suicide Severity Rating Scale)

GNX is considered to be a CNS-active intervention. GNX is related to products with an increased risk of suicidal ideation or behavior. Participants with TSC may occasionally develop suicidal ideation or behavior.

Participants being treated with GNX should be monitored appropriately and observed closely for suicidal ideation and behavior (SIB) or any other unusual changes in behavior, especially at the beginning and end of the course of intervention, or at the time of dose changes, either increases or decreases. Participants who experience signs of SIB should undergo a risk assessment. All factors contributing to SIB should be evaluated and consideration should be given to discontinuation of the study intervention.

When informed consent or assent has been given, participants or parents/caregivers/LARs of participants being treated with GNX should be alerted about the need to monitor participants for the emergence of unusual changes in behavior, as well as the emergence of SIB and to report such symptoms immediately to the study investigator.

C-SSRS will be used to rate the participant's degree of suicidal ideation on a scale ranging from "no suicidal ideation" to "active suicidal ideation with specific plan and intent" ([Posner et al, 2011](#)) (See [Section 10.17](#)). The C-SSRS will be assessed in all participants \geq 11 years of age, if appropriate, otherwise, clinical judgment will be used.

If the participant has a positive result for C-SSRS, the medical monitor should be contacted within 24 hours and the medical monitor will determine if the individual should discontinue the trial.

The C-SSRS (baseline form) will be completed at Visit 2 (baseline), while the C-SSRS (since previous visit) will be completed at Visit 4 (Week 1), Visit 8 (Week 5), Visit 9 (Week 9), and Visit 12 (Week 16). Participants who do not continue in the OLE will have their final C-SSRS assessment at their end of study visit, Visit 13A, on Week 20.

Participants who continue in the OLE will also have the C-SSRS conducted at Visit 15 (Week 18) and Visit 17 (Week 20).

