10.17 Appendix 17: Columbia-Suicide Severity Rating Scale (C-SSRS)

COLUMBIA-SUICIDE SEVERITY RATING SCALE (C-SSRS)

Baseline

Version 1/14/09

Posner, K.; Brent, D.; Lucas, C.; Gould, M.; Stanley, B.; Brown, G.; Fisher, P.; Zelazny, J.; Burke, A.; Oquendo, M.; Mann, J.

Disclaimer:

This scale is intended to be used by individuals who have received training in its administration. The questions contained in the Columbia-Suicide Severity Rating Scale are suggested probes. Ultimately, the determination of the presence of suicidal ideation or behavior depends on the judgment of the individual administering the scale.

*Definitions of behavioral suicidal events in this scale are based on those used in **The Columbia Suicide History Form**, developed by [name] and [name], Conte Center for the Neuroscience of Mental Disorders (CCNMD), New York State Psychiatric Institute, [name]. (Oquendo M. A., Halberstam B. & Mann J. J. Risk factors for suicidal behavior: utility and limitations of research instruments. In M.B. First [Ed.] Standardized Evaluation in Clinical Practice, pp. 103 -130, 2003.)*

For reprints of the C-SSRS contact [name]., New York State Psychiatric Institute, [name]; inquiries and training requirements contact [contact]

© 2008 The Research Foundation for Mental Hygiene, Inc.

SUICIDAL IDEATION		Lifetime: Time He/She Felt Most Suicidal																		

Ask questions 1 and 2. If both are negative, proceed to "Suicidal Behavior" section. If the answer to question 2 is "yes", ask questions 3, 4 and 5. If the answer to question 1 and/or 2 is "yes", complete "Intensity of Ideation" section below.
 
1. Wish to be Dead Subject endorses thoughts about a wish to be dead or not alive anymore, or wish to fall asleep and not wake up. Have you wished you were dead or wished you could go to sleep and not wake up?
 
If yes, describe:
			Yes  No 																	

2. Non-Specific Active Suicidal Thoughts General, non-specific thoughts of wanting to end one's life/commit suicide (e.g., "I've thought about killing myself") without thoughts of ways to kill oneself/associated methods, intent, or plan. Have you actually had any thoughts of killing yourself?
 
If yes, describe:
		Yes  No 																		

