
The following features should be rated with respect to the most severe type of ideation (i.e., 1-5 from above, with 1 being the least severe and 5 being the most severe). Ask about time he/she was feeling the most suicidal.
 
Most Severe Ideation: _____
 
  
 Type # (1-5)	Description of Ideation	Most Severe	
   
 Frequency	How many times have you had these thoughts? (1) Less than once a week (2) Once a week (3) 2-5 times in week (4) Daily or almost daily (5) Many times each day	_____	
 
 Duration	When you have the thoughts, how long do they last? (1) Fleeting - few seconds or minutes (4) 4-8 hours/most of day (2) Less than 1 hour/some of the time (5) More than 8 hours/persistent or continuous (3) 1-4 hours/a lot of time	_____	
 
 Controllability	Could/can you stop thinking about killing yourself or wanting to die if you want to? (1) Easily able to control thoughts (4) Can control thoughts with a lot of difficulty (2) Can control thoughts with little difficulty (5) Unable to control thoughts (3) Can control thoughts with some difficulty (6) Does not attempt to control thoughts	_____	
 
 Deterrents	Are there things - anyone or anything (e.g., family, religion, pain of death) - that stopped you from wanting to die or acting on thoughts of committing suicide? (1) Deterrents definitely stopped you from attempting suicide (4) Deterrents most likely did not stop you (2) Deterrents probably stopped you (5) Deterrents definitely did not stop you (3) Uncertain that deterrents stopped you (6) Does not apply	_____	
 
 Reasons for Ideation	What sort of reasons did you have for thinking about wanting to die or killing yourself? Was it to end the pain or stop the way you were feeling (in other words you couldn't go on living with this pain or how you were feeling) or was it to get attention, revenge or a reaction from others? Or both? (1) Completely to get attention, revenge or a reaction from others (4) Mostly to end or stop the pain (you couldn't go on living with the pain or how you were feeling) (2) Mostly to get attention, revenge or a reaction from others (5) Completely to end or stop the pain (you couldn't go on living with the pain or how you were feeling) (3) Uncertain that deterrents stopped you (6) Does not apply	_____	
  
		Type # (1-5)	Description of Ideation	Most Severe	Frequency	How many times have you had these thoughts? (1) Less than once a week (2) Once a week (3) 2-5 times in week (4) Daily or almost daily (5) Many times each day	_____	Duration	When you have the thoughts, how long do they last? (1) Fleeting - few seconds or minutes (4) 4-8 hours/most of day (2) Less than 1 hour/some of the time (5) More than 8 hours/persistent or continuous (3) 1-4 hours/a lot of time	_____	Controllability	Could/can you stop thinking about killing yourself or wanting to die if you want to? (1) Easily able to control thoughts (4) Can control thoughts with a lot of difficulty (2) Can control thoughts with little difficulty (5) Unable to control thoughts (3) Can control thoughts with some difficulty (6) Does not attempt to control thoughts	_____	Deterrents	Are there things - anyone or anything (e.g., family, religion, pain of death) - that stopped you from wanting to die or acting on thoughts of committing suicide? (1) Deterrents definitely stopped you from attempting suicide (4) Deterrents most likely did not stop you (2) Deterrents probably stopped you (5) Deterrents definitely did not stop you (3) Uncertain that deterrents stopped you (6) Does not apply	_____	Reasons for Ideation	What sort of reasons did you have for thinking about wanting to die or killing yourself? Was it to end the pain or stop the way you were feeling (in other words you couldn't go on living with this pain or how you were feeling) or was it to get attention, revenge or a reaction from others? Or both? (1) Completely to get attention, revenge or a reaction from others (4) Mostly to end or stop the pain (you couldn't go on living with the pain or how you were feeling) (2) Mostly to get attention, revenge or a reaction from others (5) Completely to end or stop the pain (you couldn't go on living with the pain or how you were feeling) (3) Uncertain that deterrents stopped you (6) Does not apply	_____	

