Definitions of behavioral suicidal events in this scale are based on those used in ***The Columbia Suicide History Form***, developed by [name] and [name], Conte Center for the Neuroscience of Mental Disorders (CCNMD), New York State Psychiatric Institute, [name]. (Oquendo M. A., Halberstam B. & Mann J. J., Risk factors for suicidal behavior: utility and limitations of research instruments. In M.B. First [Ed.] Standardized Evaluation in Clinical Practice, pp. 103-130, 2003.)

For reprints of the C-SSRS contact [name]., New York State Psychiatric Institute, [name]; inquiries and training requirements contact [contact]

© 2008 The Research Foundation for Mental Hygiene, Inc.

SUICIDAL IDEATION		Since Last Assessment		

Ask questions 1 and 2. If both are negative, proceed to "Suicidal Behavior" section. If the answer to question 2 is "yes", ask questions 3, 4 and 5. If the answer to question 1 and/or 2 is "yes", complete "Intensity of Ideation" section below.
				

1. Wish to be Dead Subject endures thoughts about a wish to be dead or not alive anymore, or wish to fall asleep and not wake up. Have you wished you were dead or wished you could go to sleep and not wake up?
 
If yes, describe:
		Yes  No 		

2. Non-Specific Active Suicidal Thoughts General, non-specific thoughts of wanting to end one's life/commit suicide (e.g., "I've thought about killing myself") without thoughts of ways to kill oneself/associated methods, intent, or plan during the assessment period. Have you actually had any thoughts of killing yourself?
 
If yes, describe:
		Yes  No 		

3. Active Suicidal Ideation with Any Methods (Not Plan) without Intent to Act Subject endures thoughts of suicide and has thought of at least one method during the assessment period. This is different than a specific plan with time, place or method details worked out (e.g., thought of method to kill self but not a specific plan). Includes person who would say, "I thought about taking an overdose but I never made a specific plan as to when, where or how I would actually do it... and I would never go through with it." Have you been thinking about how you might do this?
 
If yes, describe:
		Yes  No 		

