6.5. Columbia-Suicide Severity Rating Scale (C-SSRS)

The Columbia-Suicide Severity Rating Scale (C-SSRS) is a patient questionnaire that evaluates suicidal ideation and behaviors. The results (yes/no) from the 5 questions under suicidal ideation and the 5 questions under suicidal behavior will be summarized at baseline and post baseline using percentages and counts. The denominator for percentages will be the number of subjects with a C-SSRS assessment at baseline or at any time post baseline. The post-baseline by-question summary will list a subject as "yes" if they selected yes at any time after baseline.

The C-SSRS suicidal behavior and suicidal ideation scores recorded at baseline and any changes in post-baseline scores from the previous visit will be summarized descriptively by visit, including the number and percentage of subjects reporting any suicidal behavior and any suicidal ideation as defined in Table 5. Adult and pediatric C-SSRS data will be summarized separately.

C-SSRS data collected, including scores for suicidal ideation, intensity of ideation and actual suicide attempts, will be listed by patient and visit.

Table 5: C-SSRS Categories for Analysis

Category	C-SSRS Item response is "YES"
Suicidal behavior	Preparatory acts or behavior
	Aborted attempt
	Interrupted attempt
	Actual attempt
	Complete suicide
Suicidal ideation	Wish to be dead
	Non-specific active suicidal thoughts
	Active suicidal ideation with any methods (not plan) without intent to act
	Active suicidal ideation with some intent to act, without specific plan
	Active suicidal ideation with specific plan and intent
Non-suicidal self-injurious behavior	Non-suicidal self-injurious behavior

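### Read plainly, SAP 6.5 compares the first post-baseline C-SSRS with a lifetime-worst baseline, so decreases at that visit reflect the recall window; and no table splits post-baseline suicidality by lifetime history.

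*SAP*

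**What the plan says.** SAP 6.5 plans four C-SSRS outputs:

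- yes/no counts per question, at baseline and post-baseline, where a participant is a post-baseline yes "if they selected yes at any time after baseline";
- a by-visit summary of baseline scores and of change: "any changes in post-baseline scores from the previous visit will be summarized descriptively by visit";
- by-visit counts of any ideation and any behaviour, using the categories in SAP Table 5;
- listings by patient and visit.

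Protocol 10.17 contains two different forms. The baseline form heads its ideation section "Lifetime: Time He/She Felt Most Suicidal", and its intensity section instructs the rater: "Ask about time he/she was feeling the most suicidal". Its behaviour section is also lifetime. The follow-up form heads both sections "Since Last Assessment".

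Protocol 8.3.5 places the baseline form at Visit 2 and the follow-up form at Visits 4, 8, 9 and 12. The schedule of activities shows no C-SSRS at screening or at phone Visit 3. The general baseline rule in SAP 5.2 (last value before first dose) also selects the Visit 2 form.

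**The concern.** At Visit 4 the only earlier C-SSRS is the lifetime form. A change from the previous visit then sets about a week of recall against a lifetime maximum. A participant with past ideation and a quiet first week looks improved, although nothing need have changed. A Week 1 recurrence no worse than the lifetime worst looks unchanged or improved. Such participants can enrol: exclusion criterion 16 removes current suicidality and attempts in the past 6 months, but not older history.

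The second gap does not depend on how the change sentence is read. The planned tables give baseline and post-baseline counts side by side but never cross them. The treatment-emergent definition in SAP 6.1 (onset or worsening on drug) does not separate first-ever from recurrent events either. SAP 6.2 plans baseline-to-worst shift tables for laboratory data; SAP 6.5 plans none for the C-SSRS.

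This matters because the protocol itself says that "GNX is related to products with an increased risk of suicidal ideation or behavior". Whether an on-drug event was new for that participant is a natural safety question, and a reader would have to answer it from listings.

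**Working it through.** The plan states no figure on this point, so the check is a side-by-side reading followed by an illustration.

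**1. Recall windows**

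| Rating | Form | Window |
|---|---|---|
| Visit 2 | Baseline | Lifetime, worst point |
| Visit 4 (Week 1 ± 1 day) | Follow-up | Since Visit 2, about 6 to 8 days |
| Visits 8, 9, 12 | Follow-up | Since the previous rating |

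Only the first post-baseline step mixes forms. Later steps compare like with like, over unequal intervals. One of the four double-blind post-baseline ratings is therefore affected, normally Visit 4.

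**2. What each Visit 4 change means** (current status against Visit 2)

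- Lifetime history, no Week 1 ideation: a decrease. Artefact of the window.
- Lifetime history, Week 1 ideation no worse than the lifetime worst: no change or a decrease, although it is a recurrence on drug.
- No history and Week 1 ideation, or Week 1 above the lifetime worst: an increase. Readable as first-ever or worst-ever.

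The same holds if change means yes/no status and not a subtracted score: yes-to-no is the artefact, no-to-yes is first-ever.

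**3. Direction of net change (assumed rates)**

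Let h be the share with lifetime ideation. Take first-ever Week 1 ideation of 1% among those without history and recurrence of 10% among those with it. Net change = 0.10h + 0.01(1 − h) − h.

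- h = 5%: 0.5% + 0.95% − 5% = −3.55 points
- h = 20%: 2% + 0.8% − 20% = −17.2 points

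The summary falls even though new ideation has appeared.

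**4. How many people (assumed rates)**

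The documents give neither ideation rates nor the number aged 11 or older, the age from which the C-SSRS is normally given. Assume 25%, 50% or 75% of the 128 randomized are rated (n = 32, 64, 96), h = 5–20%, and Week 1 ideation among those with history p = 5–20%. Both arms together:

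| n | Recurrence shown as unchanged or improved, at most n·h·p | No Week 1 ideation, reads as improved, n·h·(1 − p) |
|---|---|---|
| 32 | 0.08 to 1.28 | 1.28 to 6.08 |
| 64 | 0.16 to 2.56 | 2.56 to 12.16 |
| 96 | 0.24 to 3.84 | 3.84 to 18.24 |

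In the last column the low end uses h = 5%, p = 20% and the high end h = 20%, p = 5%.

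**5. Why separate counts do not identify new cases**

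Suppose 6 of 64 are yes at baseline and 3 of 64 are yes afterwards. All three may come from the six (0 new) or none may (3 new). The two margins allow anything from 0 to 3.

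**The case against.** The strongest reply is that the change sentence need not include Visit 2. It speaks of post-baseline scores and can be read as covering only pairs of post-baseline visits, in which case the first part of the point disappears. The items are yes/no, and SAP 6.3 uses similar language for examination findings, which suggests status changes and not subtraction. This stands as a possible reading. SAP 6.5 has no formula to select it, however, and reading change as status does not remove the mismatch if Visit 2 is included.

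A reader might infer that the Visit 4 change summary is wholly uninterpretable. The documents do not support that: a rise above a lifetime worst has a clear meaning. On the plain reading, changes shown by direction would even give some information on new onset at Visit 4. From Visit 8 on they would not, because a no-to-yes step against a since-last-assessment form may be a recurrence.

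A reader might also infer that events are hidden or the arm comparison biased. Neither follows. The any-time counts, by-visit counts and listings use no change score and keep every event. Both arms complete the same forms under randomization, so the artefact is equal in expectation. Participant protection does not run through this table: after a positive result, "the medical monitor should be contacted within 24 hours".

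Finally, a split by history will give sparse cells in a trial of about 128, and listings do contain the information. That is a fair cost, but listings leave the comparison by arm to be assembled by hand.

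**Conclusion.** The point holds, as a minor one. On the plain reading of SAP 6.5, decreases and net within-arm change at the first post-baseline C-SSRS reflect a change of recall window and should not be read as improvement; increases can be read. This part rests on Visit 2 counting as the previous visit, which the text allows but does not settle.

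The absence of any table crossing post-baseline suicidality with lifetime history over the double-blind phase holds on either reading.

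The affected rating also falls at low exposure: under Protocol 6.1 participants are on 8–10% of target dose until the first step up on Day 7. The counts of people above are an illustration under assumed rates, not a frequency estimate. No endpoint, test or participant safeguard is affected.

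**What to change.** In SAP 6.5, state that no change is computed against the lifetime baseline form: the change-from-previous-visit summary starts after the first post-baseline rating, or is dropped. Keep the planned counts and listings as they are.

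Add one descriptive table by arm for the double-blind phase: worst post-baseline ideation category and worst post-baseline behaviour category, each against lifetime history from the baseline form.

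The cost is one sentence and one table. All the data are already collected, and no visit or analysis changes. The downside is sparse cells, so the table should be presented as counts without testing and read alongside the listings.

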6.6. Pregnancies

Any reported positive pregnancy results or reported pregnancies will be listed.

6.7. Tanner Staging

The Tanner scale is a scale of physical development in children, adolescent and adults. Patients will be rated as Tanner I, Tanner II, Tanner III, Tanner IV or Tanner V at baseline and end of the study. The number and percentage of patients in each category will be summarized and listed by visit.

7. APPENDIX

The following analysis will be included for the submission to EMA.

- The primary endpoint analysis will be based on the maintenance period only.
- All secondary endpoints analyses will be based on the maintenance period only.

8. SUMMARY OF MAJOR CHANGES IN THE PLANNED ANALYSES

The ITT definition is updated in this SAP.

• Intent-to-treat (ITT) Set – Includes all randomized participants, who dosed and had at least one post-baseline efficacy assessment. Participants will be summarized within the treatment group to which they were randomized. This set will be used for efficacy analyses.

In protocol, it was:

• All randomized participants. Participants will be summarized within the treatment group to which they were randomized. This population will be used for efficacy analyses.

Signature Page for VV-CLIN-000496 v3.0

Approval Task Task	Biometrics
Verdict: Approved	20-Aug-2024 19:42:19 GMT+0000
Approval Task Task	Clinical
Verdict: Approved	21-Aug-2024 00:05:24 GMT+0000
Approval Task Task	Biometrics
Verdict: Approved	21-Aug-2024 05:15:00 GMT+0000

Signature Page for VV-CLIN-000496 v3.0
